2.1 Allocated treatment

All patients during the study part 2 are treated with fingolimod 0.5 mg per day, even though patients may have been assigned a different dose (5 mg, 1.25 mg) in their initial fingolimod trial. Unless otherwise specified, all summaries will only present the “fingolimod 0.5 mg” group, which indicates the dose level used during the study part 2. For adverse events by yearly interval, additional summaries will be provided by “highest fingolimod dose 0.5 mg” group, which indicates the subjects’ highest fingolimod dose throughout all fingolimod trials.

2.2 Precision rules

Whenever possible, the minimum and maximum values of the data will be presented to the same precision as the raw data; the mean, median, quartile 1 (Q1), and quartile 3 (Q3) will

be presented to one more decimal place, and standard deviation will be presented to two more decimal places than the raw data.

2.3 Time frames, baseline, and visit windows

This section defines the study and data time frames, baseline, and rules for visit windows.

2.3.1 Database lock for Study part 2

The analyses specified in this document include data from study part 2 with a database lock planned around December 2018/January 2019. All qualified patients will participate until their scheduled visit closest to 30-Jun-2018 (+/- 3 months), which gives time for one follow-up study visit 3-months post last dose of fingolimod, for patients who discontinuing or completing the study after entering part 2 and who do not continue on commercial Gilenya.

2.3.2 Study day

The day of first administration of any dose of fingolimod study drug is defined as **Day 1**. Day 1 does not need to occur in the study part 2.

All other study days will be labeled relative to Day 1. Thus, study day for a particular event date on or after Day 1 is calculated as: $(Date\ of\ event - Date\ of\ first\ dose\ of\ fingolimod\ study\ drug + 1)$. An event that occurs prior to Day 1 is calculated as: $(Date\ of\ event - Date\ of\ first\ dose\ of\ fingolimod\ study\ drug)$.

In addition to calculating study day with respect to the first dose date of fingolimod drug across all studies, study day will also be calculated relative to the first dose date of fingolimod during the study part 2.

The number of days after permanent study drug discontinuation will be calculated as $(Date\ of\ event - Date\ of\ last\ dose\ of\ fingolimod\ study\ drug)$.

The duration of an event will be calculated as $(Event\ end\ date - Event\ start\ date + 1)$. Day 0 will not be used.

2.3.3 Baseline and post-baseline

For the summary of change from baseline in vital signs, the baseline is defined as end of study visit from study part 1 or last assessment of that patient (excluding follow-up) in extension study part 1 if the subject's end of study visit is missing.

The baseline relative to first dose of fingolimod among all studies a subject has participated in, which is defined as the last available measurement made prior to administration of the first dose of fingolimod, will be used for efficacy summaries.

The baseline relative to first dose of study drug in the core study (e.g. demographic information, core baseline characteristics) is also used for mentioned sections.

Post-baseline assessments are assessments made after the baseline assessment.

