## **9 Data analysis**

Unless otherwise mentioned, all data collected from the first dose of fingolimod in the original core/extension studies, if available, and in this long-term follow-up study will be analyzed to evaluate the long-term safety, tolerability, and effectiveness of fingolimod 0.5 mg/day in patients with MS. The baseline relative to the first dose of fingolimod (FDF baseline) will be used where change from baseline is analyzed. All the summaries will be provided by the highest assigned fingolimod dose, (i.e., fingolimod 0.5 mg/day) and any dose of fingolimod.

During Study Part Two, only adverse events, first dose monitoring, vital signs, Ophthalmological exam/OCT, and relapse are collected. The analysis including data from Study Part Two will be specified in the relevant sections.

The follow-up data after discontinuation of the study treatment in Study Part One or Study Part Two will also be summarized where appropriate.

Summary statistics for continuous variables will include N, mean, standard deviation, minimum, lower quartile, median, upper quartile and maximum.

Summary statistics for discrete variables will be presented in terms of absolute and relative frequencies. AE incidence adjusted by exposure is also used to evaluate the risk over time and presented as number of patients experiencing at least one event per 100 patient years of the at-risk population.

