#### **9.4.1.3 Vital signs**

Vital sign data collected up to the end of Study Part One will be summarized as descriptive statistics for change from FDF baseline value. The incidence rates of notable vital sign abnormalities will be summarized.

A listing of vital sign data for patients with abnormal findings will be provided.

The same analysis including data collected during the Study Part Two will be conducted for the subgroup of patients who entered Study Part Two.

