2.1 Allocated treatment

All patients during the long-term follow-up study are treated with fingolimod 0.5 mg per day. The summaries for data collected during the long-term follow-up study part I will only present one total group (the same as fingolimod any dose). However, patients may have been assigned a different dose (5 mg, 1.25 mg) in their initial fingolimod trial. The summaries for data collected from first dose of fingolimod among all studies will be presented by highest assigned dose of fingolimod; only two groups will be presented: fingolimod 0.5 mg and fingolimod any dose.

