9.3 Routine vital signs

Vital signs include sitting pulse rate, sitting systolic and diastolic blood pressure, and body temperature. First dose monitoring vital signs values will be excluded from routine vital signs summaries and listing.

Vital signs data will be summarized by presenting descriptive statistics for baseline, post-baseline, and change from baseline values by parameter and nominal visit. The incidence of notable vital sign abnormalities reported during the study part 2 will present the number and

percentage of patients satisfying notable criteria by nominal visit. An overall study visit will be generated to indicate any notable abnormalities from post-baseline visits (including follow-up visits). Criteria for clinically notable vital signs values are specified in Appendix A. Both summaries are based on the safety set.

Patients in the safety set with notable vital sign abnormalities will be listed. All vital sign parameters with clinically notable criteria will be listed for a particular patient and visit if at least one of the parameters shows an abnormality. The listing will also indicate whether the vital sign result was above or below the normal range.

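### The Part 2 SAP measures vital-sign change from the end of Part 1, not from the protocol's first-dose baseline, so its change tables omit any change that arose before that visit

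*SAP*

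**What the plan says.** Protocol section 9 gives a general rule: "The baseline relative to the first dose of fingolimod (FDF baseline) will be used where change from baseline is analyzed". Section 9.4.1.3, on vital signs, applies it: "Vital sign data collected up to the end of Study Part One will be summarized as descriptive statistics for change from FDF baseline value". It then extends the analysis: "The same analysis including data collected during the Study Part Two will be conducted for the subgroup of patients who entered Study Part Two". Section 9.4.1 assigns analyses that start from the first fingolimod dose to the fingolimod safety set.

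The Part I SAP follows this. Its default baseline is the FDF baseline (2.3.3), and its routine vital-sign summaries use the fingolimod safety set (9.3).

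The Part 2 SAP does not. For vital-sign change, section 2.3.3 says "the baseline is defined as end of study visit from study part 1", with the last Part 1 assessment (follow-up excluded) as a fallback. The FDF baseline is defined in the same section but "will be used for efficacy summaries". Section 9.3 tabulates baseline, post-baseline and "change from baseline values by parameter and nominal visit", on the safety set, which under section 2.5 generally covers Part 2 data only. Appendix A sets notable limits of two kinds: absolute ones, and changes from a baseline that it does not name. No reason for the departure appears in the text supplied.

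**The concern.** The two documents give different reference points for the same analysis, and the SAP's is an on-treatment value. The Part I SAP notes that "All patients during the long-term follow-up study are treated with fingolimod 0.5 mg per day", so apart from interruptions patients were taking the drug when this baseline was measured.

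The primary objective is long-term safety and tolerability, and protocol section 1.1 lists hypertension among events more common on fingolimod than on placebo. Vital signs are also the main routine quantitative safety measure left in Part 2: laboratory results are not entered in the database, and dose-monitoring ECGs are only listed. At stake is whether any planned table shows how far blood pressure at Part 2 visits has moved from its pre-treatment level in these patients. As planned, none does.

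**Working it through.** The study is descriptive, so there is no sample size, power or effect figure to reproduce. The check sets the texts side by side, uses one identity, and adds an illustration.

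**1. Side by side**

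| Item | Protocol 9, 9.4.1, 9.4.1.3 | Part I SAP 2.3.3, 9.3 | Part 2 SAP 2.3.3, 2.5, 9.3 |
|---|---|---|---|
| Baseline for vital-sign change | FDF | FDF | End of Part 1 |
| Data span | First dose onward, extended to Part Two data for Part Two entrants | First dose to end of Part 1 | Generally Part 2 only |
| Analysis set | Fingolimod safety set | Fingolimod safety set | Safety set |

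The Part I analysis stops at the end of Part 1, and its subgroups (section 2.5.1) do not separate the patients who went on to Part 2. Change from first dose to a Part 2 visit is therefore in neither plan.

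**2. What drops out**

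For each patient:

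change(FDF to Part 2 visit) = change(FDF to end of Part 1) + change(end of Part 1 to Part 2 visit)

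The Part 2 tables keep the second term and drop the first. For example, a rise of 5 mmHg by the end of Part 1 and a further 2 mmHg in Part 2 is 5 + 2 = 7 mmHg from FDF baseline, but 2 mmHg in the Part 2 table.

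**3. Relative notable limits**

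Appendix A includes a systolic increase of at least 20 mmHg from baseline. Section 2.3.3 introduces its baseline for the summary of change and gives no other for vital signs, so the same baseline probably applies. If so, a patient 20 mmHg above the pre-treatment level but stable since the end of Part 1 does not meet the increase limit. A patient whose pressure falls back by 20 mmHg to the pre-treatment level meets the decrease limit.

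**4. Illustration of size**

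The documents give neither a mean rise nor an SD. Assume a mean systolic rise of 3 mmHg before the end of Part 1, none after, normal changes, and the same SD σ from either baseline. Then P(change ≥ 20) = 1 − Φ((20 − μ)/σ), with μ = 3 from FDF baseline and μ = 0 from the end of Part 1.

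| σ (mmHg) | FDF: (20 − 3)/σ | Share | End of Part 1: 20/σ | Share |
|---|---|---|---|---|
| 10 | 1.70 | 4.5% | 2.00 | 2.3% |
| 12 | 1.42 | 7.8% | 1.67 | 4.8% |
| 14 | 1.21 | 11.2% | 1.43 | 7.7% |

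The gaps are 4.5 − 2.3 = 2.2, 7.8 − 4.8 = 3.0 and 11.2 − 7.7 = 3.5 percentage points. Varying the assumed rise from 1 to 5 mmHg gives:

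| σ (mmHg) | FDF | End of Part 1 |
|---|---|---|
| 10 | 2.9–6.7% | 2.3% |
| 12 | 5.7–10.6% | 4.8% |
| 15 | 10.3–15.9% | 9.1% |

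If increases and decreases of at least 20 mmHg are counted together, a 3 mmHg rise gives 5.5% against 4.6% (σ = 10), 10.6% against 9.6% (σ = 12) and 16.3% against 15.3% (σ = 14). The gap is then about 1 percentage point.

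**The case against.** A reader might infer that the reset baseline hides any blood-pressure rise caused by fingolimod, or that Part 2 loses its long-term safety question. The documents do not support either reading:

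- Only the component up to the end of Part 1 leaves the change columns. A further rise during Part 2 still shows.
- Raw baseline and post-baseline values are tabulated, and the absolute limits (systolic 160, diastolic 100 mmHg) do not depend on a baseline.
- Protocol Appendix 5 requires new or worsened hypertension to be reported as an adverse event. Part 2 SAP 9.1.2.2 summarises adverse events by year since first fingolimod dose, through Part 2.
- The Part I SAP reports change from FDF baseline up to the end of Part 1, so an earlier rise appears there, though not separately for Part 2 entrants.
- The study has one arm. Change over many years also reflects ageing and treatment of hypertension, so neither baseline yields a causal effect.
- Protocol Appendix 4 describes the pulse effect as a fall that reverses within a month, so the point mainly concerns blood pressure.

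Two further objections stand as limits. That Appendix A uses the end-of-Part-1 baseline is an inference. The illustration rests wholly on assumed inputs, places the whole rise before Part 2, and uses one SD for differences spanning very different periods; its larger gap applies only if increases are reported separately, which the SAP does not state.

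It can also be said that Part Two was added largely to continue access to the drug and collects limited safety data. That may explain a lighter analysis, but protocol 9.4.1.3 still asks for this one, and the SAP gives no reason for replacing it.

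**Conclusion.** The point holds as a departure from the protocol with a bounded consequence. The Part 2 change tables omit vital-sign change, mainly in blood pressure, between first dose and the end of Part 1, and no planned table gives change from first dose to Part 2 visits. This follows from the texts and the identity, without assumptions. The effect on the relative notable limits is conditional on Appendix A using the same baseline.

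The size cannot be obtained from the documents. With the 3 mmHg rise and SD 10–14 mmHg assumed above, the share with an increase of at least 20 mmHg is 2.2 to 3.5 percentage points lower than from FDF baseline, and the difference is about 1 point if both directions are pooled. The analysis is descriptive and blood-pressure information survives elsewhere, so the SAP should be corrected, but the safety evaluation does not fail because of this.

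**What to change.** In Part 2 SAP 2.3.3 and 9.3:

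1. Summarise vital-sign change, and apply the relative notable limits, from FDF baseline for patients who entered Part 2.
2. Use the fingolimod safety set with data from first dose through Part 2. Changing the baseline alone would leave the tables on Part 2 data and would not reproduce the analysis in protocol 9.4.1 and 9.4.1.3.
3. State in Appendix A which baseline its relative limits use.
4. Keep change from the end of Part 1 as a labelled supplementary column. It answers a separate and useful question: what happened during Part 2.

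The cost is SAP wording and a small amount of extra programming. FDF vital-sign baselines are already used for Part I, and the Part 2 SAP already defines both the FDF baseline and the fingolimod safety set. No new data are needed.

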2.3.4 Variables Summarized by Visits

Below are the visit windowing rules used for visits as defined in the Virtual Data Warehouse (VDW) RAP M4 draft version 4.3.

Visit windows will be widely used to align visits across studies. They are based on the assessment schedule of the pivotal studies and comprise a set of days around the nominal visits. The same visit windows will apply to all studies. Visit windows are non-overlapping; all together they cover the entire study period. Generally, visit-windows are not symmetrical around the nominal visit day. Among all the analysis, only efficacy summaries will use visit window. Safety summaries will be based on nominal visits.

Visit windows will be used to present summary statistics by visit. Efficacy data sets consider only scheduled visits. For efficacy analysis, if multiple assessments are available within a visit window, the record closest to the target day will be selected (if more than one assessment is equidistant to the target day, the later assessment will be used).

Unless otherwise specified, the following visit windows are derived with respect to the first dose date of fingolimod among all studies.

Table 1 Visit-windows for efficacy data (MS relapse)

Visit	Start day (time)	Target Day (time)	End day (time)
Month 3	1	91	136
Month 6	137	182	273
Month 12	274	365	547
Month 24	548	730	912
Year 3 (M36)	913	1095	1278
Year 4 (M48)	1279	1461	1643
Year 5 M(60)	1644	1826	2008
Year 6 (M72)	2009	2191	2373
Year 7 (M84)	2374	2556	2739
Year8 (M96)	2740	2922	3104
Year 9	3105	3287	3469
Year 10	3470	3652	3834
Year 11	3835	4017	4200
...		every 12 months	
Month X (row i)	$S_i = \text{Integerpart}((D_i + D_{i-1}) / 2) + 1$	$D_i = \text{Integerpart}(X * 365.25 / 12)$	$E_i = \text{Integerpart}((D_{i+1} + D_i) / 2)$
...	...	Every 12 months	...
Month X (last row)	S_{last}	D_{last}	$E_{\text{last}} = D_{\text{last}} + (D_{\text{last}} - S_{\text{last}})$

- Day 1 is defined as the first dose day of fingolimod among all studies.
- If multiple assessments are available within a visit window, the record closest to the target day will be selected (if more than one assessment is at the same distance to the target day, the later one will be used for summary statistics (after unscheduled visits are excluded).

Table 2 Follow-up visit windows for efficacy data (MS relapse)

Visit label	Start day (time)	Target Day (time)	End day (time)
FU (Month 3)	Day 1 p.l.d	Day 90 p.l.d	
- Follow-up visit windows are defined relative to study drug discontinuation in the respective pool (unscheduled visits will be excluded). - p.l.d = post last dose. - Day 1 p.l.d is defined as the first day after the last dose day of fingolimod .			

2.4 Imputation of Incomplete Dates

Incomplete or partial dates will be imputed (where appropriate, and will follow Virtual Data Warehouse (VDW) imputation rules – refer to VDW MAP M8) to decide on the inclusion or exclusion of related events in the summary tables. Each incomplete date will be split into its day, month, and year components, and an imputation rule will be applied. However in data listings, the dates as available in the database should be listed (without imputation).

General imputation rules from the VDW MAP M3, draft version 3.0 are given below.

Specific imputation rules may apply to certain panels (e.g. concomitant medications) and are described in the relevant sections. If no imputation rules are described then the general imputation rules apply to partially missing or impossible dates:

- If the year is missing or impossible (e.g. 12-Jan-1911), then the date will be imputed as missing.
- If the year is not missing and possible, but the month is impossible or missing (e.g. 17-XXX-2010), then the year will be kept and July 1st will be imputed (1-July-2010).
- If the year and the month are not missing and possible, but the Day is impossible or missing (e.g. 31-FEB-2009), then the year and month will be kept, the 15th will be imputed (15-FEB-2009).

2.5 Analysis sets

The following analysis sets will be defined. Analyses done on the fingolimod safety set and fingolimod full analysis set summarize all data starting from first dose of fingolimod among all studies, while other analysis sets generally summarize all data from the study part 2 only.

- **Enrolled set:** The enrolled set will include all patients who entered the study part 2 (excludes long-term extension study screen failures), but will exclude patients with protocol deviation severity code of 8 (8=exclude from all analyses) in the study part 2.
- **Safety set:** The safety set is a subset of the fingolimod safety set and will include all patients who entered the study part 2 and received at least one dose of fingolimod in any study, but will exclude patients with protocol deviation severity codes of 5 (5=exclude from all safety analyses) and 8 (8=exclude from all analyses) in the study part 2. Note that all data reported in the study part 2 will be analyzed, including assessments or events which started before the study part 2, unless otherwise specified. For example, adverse events which may have been continuing at the end of the long-term follow-up

study part 1 may be recorded in the study part 2 database with updated end date. These adverse events will be reported in listings and summarized if event occurs after first dose of fingolimod among all studies.

- **Fingolimod safety set:** The fingolimod safety set will include all patients who entered the study part 2 and received at least one dose of fingolimod in any study, but will exclude patients with protocol deviation severity codes of 5 (5=exclude from all safety analyses) and 8 (8=exclude from all analyses) during the core study prior to entry to the long-term follow-up study part 1. For patients with such protocol deviations after the core study, record level data associated with the protocol deviations will be excluded from the analysis.
- **Fingolimod full analysis set:** The fingolimod full analysis set will include all patients who entered the study part 2 and received at least one dose of fingolimod in any study but will exclude patients with protocol deviation severity codes of 0 (0=exclude from all efficacy analyses) and 8 (8=exclude from all analyses) during the core study prior to entry to the long-term extension study part 1. For patients with such protocol deviations after the core study, record level data associated with the protocol deviations will be excluded from the analysis.
- **Follow-up set:** The follow-up set will consist of all patients in the safety set who have any follow-up visit data or at least one safety record after the study drug discontinuation. It will be used for summary of adverse events and concomitant medications with occurrences after last dose of fingolimod only.

Patient disposition, core study, protocol deviations, analysis sets, demographics, and baseline and history information will be summarized based on the enrolled set. Efficacy analyses will be summarized based on the fingolimod full analysis set. Safety summaries that include only study part 2 data will be based on safety set or follow-up set as specified.

A summary of the number and percentage of patients in each analysis set will be summarized. Percentages will be based on the enrolled set. A listing of patient assignment into each analysis set will also be displayed.

2.5.1 Subgroups

The following subgroups are defined for subject disposition and AE analysis during fingolimod treatment period:

1. Duration of fingolimod treatment up to the end of the study part 2 (yearly interval):
 - Year 1 subgroup: patients on fingolimod treatment > 0 year (≥ 1 day)
 - Year 2 subgroup: patients on fingolimod treatment > 1 year (≥ 361 days)
 - Year 3 subgroup: patients on fingolimod treatment > 2 year (≥ 721 days)
 - Year 4 subgroup: patients on fingolimod treatment > 3 year (≥ 1081 days)
 - Year 5 subgroup: patients on fingolimod treatment > 4 year (≥ 1441 days)

- Year N subgroup: patients on fingolimod treatment > N -1 year ($\geq (N - 1) \times 360 + 1$ days)

3 Protocol Deviations

The number and percentage of patients in the enrolled set with each protocol deviation in the study part 2 will be displayed by protocol deviation category. Additionally, patients with at least one protocol deviation during the study part 2 and patients with at least one protocol deviation causing exclusion from any analysis set (deviation severity codes 0, 5, or 8) will be summarized.

The protocol deviation data will be listed as well.

Additionally, the investigator comments during the study part 2 will be listed.

4 Patient Disposition

All screen failures in the study part 2 will be listed along with their primary reason for failing screening.

The number and percentage of patients who completed the study part 2, and who discontinued the study part 2, along with the primary reason for discontinuation, will be summarized for the enrolled set. The number and percentage of patients who are expected to have month 3 follow-up visit and who returned will also be summarized. The number and percentage of patients who move to commercial fingolimod after study completion will also be included.

To further evaluate the disposition within a particular fingolimod treatment duration, study completion and discontinuation will be summarized in separate tables based on patients' fingolimod exposure by cumulative yearly interval. Patients will be summarized within a particular yearly interval if they have been receiving study treatment for at least one day in that particular interval. For example: year 1 will consist of subjects on fingolimod treatment for at least 1 day; year 2 will consist of subjects on fingolimod treatment for at least 361 days, year 3 will consist of subjects on fingolimod treatment for at least 721 days and so on. For study completion, the number and percentage of patients who completed the study part 2, and who move to commercial fingolimod after study completion will be provided by yearly exposure group as defined above. For study discontinuation, the number and percentage of patients who discontinued the study part 2, along with the reason for discontinuation, and who move to commercial fingolimod after study discontinuation will be provided by yearly exposure group as defined above.

The patients who discontinued from the study part 2 and corresponding reasons will be listed for the enrolled set. Additionally, a similar listing will be provided for the enrolled set of patients from D2312 and D2402 studies who discontinued early from the study part 2.

5 Background and demographic characteristics

